2.8 STUDY ENDPOINTS

Principle Outcomes: The principle objectives for the pilot trial are to evaluate 1.) safety and efficacy and 2.) feasibility for a prehospital through in-hospital LTLR-WB resuscitation protocol that will lead to a large, multicenter clinical trial that can be performed under the requirements of *exception from informed consent for emergency research* with regulatory oversight by the Food and Drug Administration (FDA) and Title 21, Code of Federal Regulations, Section 50.24 (21 CFR 50.24).

Primary Outcome For Assessing Safety and Efficacy: The primary safety and efficacy outcome for the pilot trial will be all cause 28-day mortality. We will utilize data derived from our recently completed PAMPer trial, which utilized identical inclusion and exclusion criteria, for inhospital mortality estimates.

Primary Outcome For Assessing Feasibility and Trial Performance: The primary feasibility outcome for the pilot trial will be enrollment and accrual rate. Secondary performance and feasibility outcomes will include a) Eligibility rates; b) Adherence rates for the protocol; c) Injury and patient characteristics enrolled in the trial; d) Frequencies of proposed clinical outcomes; e) Air medical base population differences.

Secondary Clinical Outcomes Estimating Treatment Effectiveness and Safety: Over 28 days or up to discharge following randomization, we will compare: 1) Multiple Organ Failure (MOF): Organ dysfunction will be evaluated via the Denver Post-Injury Multiple Organ Failure Score and characterized as both a rate (%) and as MOF free days.^{84,85} 2) Mean Denver Post-injury MOF Score: This continuous variable will be a much more sensitive measure of organ dysfunction for the pilot trial. 3) Arrival Shock Severity: We will compare presenting base deficit,

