Sample Size Justification for Pilot Trial: Assuming a baseline in-hospital mortality risk of 33% in the control arm as was demonstrated in the recently completed PAMPer trial with all cause in-hospital mortality as the primary outcome, enrolling **56 patients in each arm, 112 total patients** and using a 2 sided alpha of 0.05, the study will have a 80% power to detect a 22% (33% to 11%) or greater difference in in-hospital mortality. Based upon current PAMPer clinical outcome data and the additional benefit attributable to LTLR-WB when it is initiated in the prehospital setting, the current proposed mortality difference is clinically meaningful and of sufficient magnitude to influence clinical practice for a pilot trial. The above sample size will provide more than sufficient power for the originally planned feasibility outcomes as we have increased our sample size by 24%. The above power analysis was generated assuming 2 sequential tests using the O'Brien-Fleming spending function to determine test boundaries which are depicted in the following table and graph.

Details	Details when Spending = O'Brien-Fleming, N1 = 56, N2 =56, P1 = 0.1100, P2 = 0.3300							
		Lower	Upper	Nominal	Inc	Total	Inc	Total
Look	Time	Bndry	Bndry	Alpha	Alpha	Alpha	Power	Power
1	0.50	-2.96259	2.96259	0.003051	0.003051	0.003051	0.164669	0.164669
2	1.00	-1.96857	1.96857	0.049002	0.046949	0.050000	0.636252	0.800921
Drift 2.	81024							

Based upon the busy air medical service at the University of Pittsburgh, the bases to be utilized for the pilot trial, 61 patients who met all inclusion and exclusion criteria for the current proposed pilot trial, were admitted to Presbyterian Hospital, consented and were enrolled (www.pamperstudy.com) over a 12 month period 6/2015-5/2016. Based upon a planned enrollment period of 2.5 years, this sample size is feasible after accounting for consent rates and exclusions.

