- 5. Adherence rates for each treatment arm of the protocol will be ascertained and recorded as the proportion of enrolled patient who adhere to each of the study arms

Interim Analysis

The main points in the interim analysis:

- 1. Monitor the eligibility, enrollment, and subject accrual as stated above.
- 2. Safety and efficacy by looking for In-hospital mortality differences between LTLR-WB and Standard of Care arms and compared these ratios using a pooled Z test of two independent proportions. Stopping rules will be used in the study interim analysis.
- 3. Survival analysis will be monitored in the interim analysis
- 4. Secondary outcomes will be checked and related 95% C.I will be estimated across the study two arms.
- 5. Unanticipated Events
- 6. Protocol deviation

Stopping rules

The following stopping rules of O'brien-Fleming boundaries will be implemented in the interim analysis:

Details wher	Spending	= O'Brien-	Fleming, N1	l = 56, N2 =	56, P1 = 0.1	100, $P2 = 0$.3300
Look Time	Lower Bndry	Upper Bndry	Nominal Alpha	Inc Alpha	Total Alpha	Inc Power	Total Power
2 1.00	-1.96857	1.96857	0.049002	0.046949	0.050000	0.636252	0.800921
Drift2.81024	4 3.5 3 2.5 1.5 1.5 1.5 1.5 0 7 2 5 0 7 7 7 7 5 7 7 7 7 7 7 7 7 7 7 7 7 7	O'Brien-F	leming Bound	daries with Al	pha = 0.05	×.	

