8. Look back procedures: Since the plasma will be tracked through the participating centers Blood Bank/Transfusion service look back/product recall procedures will be conducted as per standard protocol (**Appendix 6**).

6.4.7 Withdrawal of Subjects and Stopping Criteria:

Assuming a baseline in-hospital mortality risk of 33% in the control arm as was demonstrated in the recently completed PAMPer trial (manuscript in preparation) with all cause in-hospital mortality as the primary outcome, enrolling 56 patients in each arm, 112 total patients and using a 2 sided alpha of 0.05, the study will have a 80% power to detect a 22% (33% to 11%) or greater difference in in-hospital mortality. Based upon current PAMPer clinical

outcome data and the additional benefit attributable to LTLR-WB when it is initiated in the prehospital setting, the current proposed mortality difference is clinically meaningful and of sufficient magnitude to influence clinical practice for a pilot trial. The above sample size will provide more than sufficient power for the originally planned feasibility outcomes as we have increased our sample size by 24%. The above power analysis was generated assuming 2 sequential test are made using the O'Brien-Fleming spending function to determine test boundaries which are depicted in the following table and graph.

Details	Details when Spending = O'Brien-Fleming, N1 = 56, N2 =56, P1 = 0.1100, P2 = 0.3300							
		Lower	Upper	Nominal	Inc	Total	Inc	Total
Look	Time	Bndry	Bndry	Alpha	Alpha	Alpha	Power	Power
1	0.50	-2.96259	2.96259	0.003051	0.003051	0.003051	0.164669	0.164669
2	1.00	-1.96857	1.96857	0.049002	0.046949	0.050000	0.636252	0.800921
Drift 2.	.81024							

Discontinuation of the Clinical Trial:

The investigator may withdraw a subject from participating in this research if circumstances arise which warrant doing so. The decision may be made either to protect the subject's health and safety, or because the subject's condition did not meet certain criteria needed for study inclusion.

6.5 **RISKS MANAGEMENT PROCEDURES**

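### The only numeric stopping rule is a symmetric O'Brien-Fleming boundary, so mortality harm at the single interim must meet the same strict limit (z of 2.963) as benefit

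*Combined protocol and SAP*

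**What the plan says.** Mortality serves both as safety and as efficacy outcome. Section 2.8 states: "The primary safety and efficacy outcome for the pilot trial will be all cause 28-day mortality". Section 2.9 also names 28-day mortality. The data analysis plan inside section 6.4.2 names in-hospital mortality instead, and its interim analysis compares in-hospital mortality between the arms with a pooled Z test.

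The stopping rule for that comparison is that the "stopping rules of O'brien-Fleming boundaries will be implemented in the interim analysis". Section 2.9 describes the design as "2 sequential tests using the O'Brien-Fleming spending function to determine test boundaries", with "56 patients in each arm, 112 total patients", "using a 2 sided alpha of 0.05" and the claim that "the study will have a 80% power to detect a 22% (33% to 11%) or greater difference". The look-1 row of the table in sections 2.9 and 6.4.7 begins "1 0.50 -2.96259 2.96259 0.003051": information time, lower limit, upper limit and nominal two-sided alpha. No other numeric limit for mortality appears in the protocol.

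Alongside this rule, section 6.4.2 leaves the final decision on the monitoring plan to the DSMB. It expects the DSMB to compare adverse events by arm every six months, and to monitor primary and secondary outcomes by arm. Appendix 2 lets the DSMB recommend termination because of adverse effects, hold emergency meetings, and set its monitoring guidelines at a first meeting before the study starts.

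**The concern.** A strict early limit protects the efficacy claim: it keeps a chance early benefit from ending the trial, and it leaves almost all of the alpha for the final look. A symmetric design applies the same limit to harm, at a one-sided level of about 0.0015. Early evidence that LTLR-WB increases deaths would have to be as extreme as early evidence that it prevents them, although mortality is a named safety outcome.

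This matters here for two reasons. Patients are enrolled under exception from informed consent (sections 5.1 and 5.2), and Appendix 4 cites independent data monitoring as one of the added protections. Also, there is only one interim, so the second formal limit is applied after all 112 patients are enrolled.

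**Working it through.** **Inputs.** Section 2.9: "Assuming a baseline in-hospital mortality risk of 33% in the control arm"; 11% in the LTLR-WB arm; 56 per arm; two-sided alpha 0.05; two looks; interim at time 0.50, hence 0.50 × 56 = 28 per arm. Sections 2.9 and 6.4.7: limits ±2.96259 at look 1 and ±1.96857 at look 2. Section 6.4.2: pooled Z test. The harmful LTLR-WB mortality rates below are assumptions, shown as a range.

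**1. Reproduce the plan's design.**
- O'Brien-Fleming-type spending with 0.025 per side: 2 − 2Φ(z₀.₉₈₇₅/√0.5) = 0.0015253 per side, 0.0030506 in total, limit 2.96259. The table gives 0.003051 and 2.96259.
- Drift with pooled variance: 0.22/√(0.22 × 0.78 × 2/56) = 2.81024, as in the table.
- Bivariate normal with correlation √0.5: look-1 power 0.1647 and total power 0.8010. The table gives 0.164669 and 0.800921.

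The boundary is calculated correctly.

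**2. What the interim limit means in deaths.** Z = (p_WB − p_C)/√(p̄(1 − p̄) × 2/28). With 9/28 control deaths (32%):
- 20/28 LTLR-WB deaths: p̄ = 29/56, Z = 0.3929/0.1336 = 2.94, which does not cross 2.963.
- 21/28 LTLR-WB deaths (75%): p̄ = 30/56, Z = 0.4286/0.1333 = 3.22, which crosses.
- One-sided limits of 1.645 and 1.96 would be crossed at 16/28 (Z = 1.88) and 17/28 (Z = 2.14).

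**3. Chance of crossing on the harm side at the interim.** For each pair of true rates, the two binomial probabilities (n = 28 each) are multiplied and summed over all outcomes whose pooled Z reaches the limit. Control mortality is 33%.

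| True LTLR-WB mortality | Plan, 2.963 | Guideline 1.96 (p 0.025) | Guideline 1.645 (p 0.05) |
|---|---|---|---|
| 33% (no difference) | 0.14% | 2.6% | 5.3% |
| 43% | 1.3% | 11.5% | 18.7% |
| 50% | 4.4% | 24.2% | 34.6% |
| 55% (22 points reversed) | 8.7% | 37.0% | 48.5% |
| 66% (doubled) | 28.9% | 69.5% | 78.7% |

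At the planned benefit (11% v 33%), the 1.645 guideline raises a harm alert with probability 0.014%.

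**4. Sensitivity.** Section 2.2 also mentions overall mortality of 30%. With control mortality of 30%, the plan's limit is crossed with probability 1.4% at 40%, 9.3% at 52% and 22.5% at 60%.

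**5. Both looks together.** In 400,000 simulated trials with control mortality of 33%, the plan's harm limit was crossed at either look in 19% of trials at 43%, 44% at 50% and 65% at 55%. Most of these crossings come only at the final look.

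**6. Correlated outcomes.** Allocation is by helicopter base and month (section 2.6), and no intra-cluster correlation is given. For an assumed design effect D, the false-alert rate is about 1 − Φ(limit/√D). With D from 1.1 to 1.5, it is 3.1% to 5.5% at 1.96 and 5.8% to 9.0% at 1.645.

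**The case against.** The strongest reply is that harm monitoring is delegated to the DSMB and is not missing. The board controls the monitoring plan, sees outcomes by arm, may recommend termination and sets its guidelines before the study starts (section 6.4.2, Appendix 2). The study team also reviews the balance of benefit and risk (sections 6.4.3 and 6.4.4). This stands. A reader might infer that patients have no protection against excess deaths, or that no harm guideline exists anywhere. The documents do not support either inference, because the DSMB's own guidelines are not among them. They do show that the protocol supplies one numeric limit and no separate one for harm.

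A reader might also infer that the interim would almost never stop the trial however large the harm. That is too strong: the chance is 1% to 9% for increases of 10 to 22 points, but 29% if mortality doubles.

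Third, a symmetric boundary is a legitimate choice in a two-sided design. Crossing the upper limit there is a formal claim of harm, and the alpha covers it. This also stands, so the point concerns a design choice and not an error. A non-binding guideline makes no such claim; it prompts the board to deliberate.

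Last, much of the insensitivity comes from having only 28 patients per arm. At a 22-point harm, both looser limits still miss more often than not (crossing chances of 37.0% and 48.5%). The guideline improves detection but does not make it reliable.

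**Conclusion.** The point holds as a recommendation. The protocol's only numeric stopping rule asks for the same evidence of harm as of benefit. It would miss a full reversal of the planned effect at the interim about 91% of the time (100% − 8.7%). A one-sided guideline at p of 0.025 to 0.05 would detect that reversal roughly four to six times as often (37.0/8.7 = 4.3; 48.5/8.7 = 5.6).

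The figures assume exactly 28 evaluable patients per arm, independent outcomes and control mortality of 33%; control mortality of 30% gives the same picture. They apply to whichever mortality outcome is monitored, and the documents disagree on that: section 6.4.2 uses in-hospital mortality, while sections 2.8 and 2.9 name 28-day mortality as primary.

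**What to change.** Keep the O'Brien-Fleming limits for efficacy. Add to section 6.4.2, and to the DSMB's monitoring guidelines, a non-binding one-sided harm guideline for mortality at the interim, for example nominal p of 0.025 to 0.05 against LTLR-WB, with the level agreed with the DSMB. State that crossing it calls for DSMB deliberation and does not by itself end the trial. State also that sensitivity is limited by the interim sample size.

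Reconcile sections 2.8, 2.9 and 6.4.2 so that one mortality outcome is named for the efficacy boundary and the harm guideline.

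The work is a change of wording in the protocol and the DSMB guidelines. The statistical cost is a false alert in about 2.6% to 5.3% of trials with no true difference if patients are independent, and somewhat more if outcomes are correlated within base-months. Because the guideline is non-binding, the efficacy alpha does not change.

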6.4.3 Parameters to be Monitored by Local Study Team

The following progress will be monitored throughout the course of the research to ensure the safety of subjects as well as the integrity and confidentiality of their data.

- An evaluation of the progress of the research study, including subject recruitment and retention, and an assessment of the timeliness and quality of the data.
- A review of collected data (including adverse events, unanticipated problems, and subject withdrawals) to determine whether there is a change to the anticipated benefit-to-risk assessment of study participation and whether the study should continue as originally designed, should be changed, or should be terminated.
- An assessment of external factors or relevant information (eg. pertinent scientific literature reports or therapeutic development, results of related studies) that may have an impact on the safety and study participants or the ethics of the research study.
- A review of study procedures designed to protect the privacy of the research subjects and the confidentiality of their research data.

Summary of Reports

A summary of the data and safety monitoring meetings will be reported to the University of Pittsburgh HRPO office during annual renewal and to the NIH as required. The DSMB chair and NIH Program Officer will regularly receive reports of enrollment, demographics, AE/SAEs, and UAPs. Annual IND reports will be submitted to the FDA via the University of Pittsburgh's O3IS (Investigator-Sponsored IND and IDE Support Office).

6.4.4 Frequency of Monitoring

The Investigator will review subject safety data as it is generated. The Investigator, subinvestigators, and the research staff will meet on at least a quarterly interval during the active recruitment phase of the study to re-evaluate study goals, subject recruitment, data coding and retention, documentation and identification of adverse events, complaints and confidentiality of subjects. There will be an evaluation of the progress of the research study, including assessments of data quality, time lines, participant recruitment, accrual, and retention. The Investigator will also review the outcome and adverse event data to determine whether there is any change to the anticipated benefit-to-risk ratio of study participation and whether the study should continue as originally designed or should it be re-evaluated and changed.

6.4.5 Reportable Adverse Events

Assessing and Reporting Adverse Events (AEs): Enrolled subjects will be monitored for adverse events throughout the first 48 hours after hospital admission. Reporting forms will be submitted to the DSMB and IRB. Potential adverse events occurring within the first 48 hours after admission will be reviewed as to treatment arm and further classified by: a) Severity (life-threatening, serious, non-serious); b) Expected vs. Unexpected; and c) Related, Possibly Related, Probably Not Related, or Definitely Not Related. For serious adverse events that are related or possibly related to the study or intervention, the coordinating center will notify the IRB and the DSMB as well as additional appropriate regulatory agencies and sponsor promptly. The coordinating center will tabulate and report compliance, data quality, and non-serious adverse events on a regular basis.

Expected adverse events are commonly observed in patients who are at risk of hemorrhage following traumatic injury and may or may not be attributable to the LTLR-WB. Clinical diagnoses of pneumonia, sepsis, cerebral bleeding, stroke, seizures, surgical interventions, complications due to specific injuries as well as other major medical or surgical complications are commonly

observed in these patients. They will be recorded as noted in the hospital discharge summary as complications and will not be reported as adverse events.

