2.3 STUDY INTERVENTION

The study intervention will be the initiation of prehospital through in-hospital transfusion of LTLR-WB in patients meeting all inclusion and no exclusion criteria. Whole blood units will be obtained from a local FDA licensed blood center (LifeSource dba Central Blood Bank; Registration number: 2571073; License number: 1025).

Up to two units of LTLR-WB (O+) will be initiated in the prehospital phase of the study with an additional 6 units of LTLR-WB (O+) available during the in-hospital phase of the trial if indicated.

Study Intervention Rationale: To provide the earliest and most robust intervention with appropriate concern for blood banking resource utilization, a prehospital and in-hospital phase intervention will be utilized. As whole blood resuscitation is most pertinent to patients with acute hemorrhage, we have limited the in-hospital acute resuscitation phase time period and the additional 6 units of LTLR-WB to 4 hours post-admission. This acute phase resuscitation period definition is based upon unpublished data from the recently completed PAMPer study at our institution.⁴⁰ Over 79% of the blood products transfused in the first 24 hours occurred in the first 4 hours following admission.

Whole Blood Intervention: Blood from male only, group O+ donors will be collected using the FDA approved Terumo Imuflex® WB-SP blood bag system. With this collection system, whole

blood passes through a platelet sparing inline leukoreduction filter into a bag containing citrate phosphate dextrose solution. Male only whole blood donors will be used in order to mitigate the risk of transfusion related acute lung injury (TRALI; estimated incidence ≈1:12,000). Whole blood collected with this system can be kept as such for up to 21 days when stored between 1-6°C. Per blood bank protocol, the anti-A and anti-B antibody titers in each unit will be tested on a sample from every donor using an immediate spin saline tube method without incubation; only units where the titer of both anti-A and anti-B are <100 will be issued for the study and subsequent transfusion. All other required transmissible disease testing will also be performed on these LTLR-WB units before they are released, as per blood bank standard practice. The LTLR-WB units will have affixed on them the standardized Whole Blood product label thereby making them easily distinguishable from the other non-WB units in inventory.

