lactate and shock index (SI, heart rate/systolic blood pressure-bpm/mmHg) 4) Acute Respiratory Distress Syndrome (ARDS): We will compare pulmonary dysfunction using the Berlin definition for ARDS.⁸⁶ 5) Nosocomial Infection (NI): We will compare the incidence of pneumonia and blood stream infections. 6) Mortality: We will compare mortality rates at 3, 6 and 24 hours following arrival, all cause in-hospital and 28-day mortality. 7) Blood component transfusion and resuscitation requirements at 24 hours: We will compare overall blood component transfusion requirements and crystalloid/colloid resuscitation requirements across the two arms. 8) Acute Hemolytic Transfusion Reaction (AHTR): We will compare the incidence of AHTRs across study arms as defined by the CDC/National Healthcare Safety Network (NHSN) Hemovigilance Surveillance definition. (www.cdc.gov/nhsn) Length of hospital stay and intensive care unit stay. Length of stay and ICU resources will be descriptively compared. Patients will be followed for 28 days from admission for the 28-day mortality outcome utilizing chart review, patient contact or utilization of the social security death index for those who cannot be contacted.

Predefined Subgroup Analyses: Predefined subset analyses for the pilot trial will be performed looking at our primary outcomes (safety/efficacy and feasibility) in 1) Females > 50 years of age versus study cohort with females < 50 years excluded ; 2) Patients who ultimately did or did not require in-hospital blood transfusion; 3) Patients with and without significant traumatic brain injury (Head abbreviated injury score- AIS >2); 4) Patients enrolled from the scene of injury versus those enrolled from a referral hospital; 5) Patients that require operative intervention in the first 24 hours; 6) Those patients with a preinjury history of anticoagulation / antiplatelet therapy; 7) Patients who ultimately did or did not require massive transfusion (≥ 10 units blood in first 24 hrs) 8)Patients who did or did not receive prehospital PRBCs.

Clinical Outcome Definitions:

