6. POTENTIAL RISKS AND BENEFITS

6.1 POTENTIAL RISKS

Risks Associated With LTLR-WB: The whole blood product to be utilized starting in the prehospital environment in the pilot clinical trial is the identical product to be used in the hospital and identical to the current whole blood product that has been transfused in over 200 patients over the last 24 months at the University of Pittsburgh without evidence of complications or transfusion reactions. The primary risk with LTLR-WB is a hemolytic transfusion reaction which will be followed as an important secondary outcome. There have been no hemolytic transfusion reactions in over 200 patients transfused LTLR-WB at the University of Pittsburgh in the last 24 months. The primary risks with any blood transfusion can be found in the Circular of Information prepared jointly by AABB, the American Red Cross, America's Blood Centers, and the Armed Services Blood Program. Those primary acute immunologic complications include hemolytic transfusion reactions, immune mediated platelet destruction, febrile nonhemolytic reactions, allergic reactions, anaphylactoid reactions and transfusion-related acute lung injury (TRALI). Delayed immunologic complications include delayed hemolytic reaction, alloimmunization, posttransfusion purpura, transfusion-associated graft-vs-host disease. Nonimmunologic complications include transmission of infectious agents, bacterial sepsis, transfusion-associated circulatory overload (TACO), hypothermia and metabolic complications.

The primary risk associated with transfusion of Rh+ blood into a woman of child-bearing potential (WCP) is hemolytic disease of the fetus and newborn (HDFN) of a future pregnancy. Complications of HDFN include fetal anemia, fetal hydrops, and in the most severe cases, fetal death. However, the overall risk of poor fetal outcome in a future pregnancy for Rh- women that are administered Rh+ blood products has been estimated to be less than 0.5%⁹⁰. Of note, the incidence of a female being Rh- is only 15%. This means that the majority of WCP are at no risk of Rh mismatch. For those WCP that are at risk, the likelihood of poor fetal outcome is very small.

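### Adverse-event collection ends 48 hours after admission, so the delayed immunologic transfusion reactions listed in Section 6.1 have no prospective capture by arm after that point

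*Combined protocol and SAP*

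**What the plan says.** Section 6.4.5 states the limit twice. Collection: "Enrolled subjects will be monitored for adverse events throughout the first 48 hours after hospital admission". Review: "Potential adverse events occurring within the first 48 hours after admission will be reviewed as to treatment arm", followed by classification for severity, expectedness and relatedness.

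Section 6.1, setting out the risks of transfusion, says: "Delayed immunologic complications include delayed hemolytic reaction, alloimmunization, posttransfusion purpura, transfusion-associated graft-vs-host disease". For women of child-bearing potential given Rh-positive blood, it adds that the primary risk "is hemolytic disease of the fetus and newborn (HDFN) of a future pregnancy".

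Other outcomes run longer. Section 2.8 introduces the secondary effectiveness and safety outcomes with "Over 28 days or up to discharge following randomization, we will compare", and says of survival that "Patients will be followed for 28 days from admission for the 28-day mortality outcome". Section 6.4.2 anticipates that the DSMB will compare adverse-event rates between arms every 6 months and will also monitor the primary and secondary outcomes.

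**The concern.** The protocol names a class of harms that it labels delayed, then closes adverse-event collection two days after admission. Section 6.1 calls a hemolytic reaction the main risk of the study product and says it will be followed as a secondary outcome, yet Section 2.8 defines that outcome as the acute form only. The delayed form therefore has no defined endpoint.

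Safety is one of the principal objectives in Section 2.8, and the pilot is meant to inform a large multicenter trial. If the adverse-event table shows no difference between arms, a reader planning that trial could take it as reassurance on delayed reactions. For any that appear after 48 hours, the table would show nothing whatever the truth.

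**Working it through.** The plan gives no figure on this point to reproduce. The check compares time windows and asks, for each route by which an event could be recorded, whether it would catch a delayed immunologic reaction by arm.

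**Windows**

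1. Adverse-event window (Section 6.4.5): 48 h = 48/24 = 2 days. Outcome follow-up (Section 2.8): 28 days. Share: 2/28 = 7.1%.
2. Study-product period (Section 2.3): "we have limited the in-hospital acute resuscitation phase time period and the additional 6 units of LTLR-WB to 4 hours post-admission". The adverse-event window extends 48 − 4 = 44 h beyond it, so acute reactions are covered.
3. Last scheduled research blood sample (Section 2.8): 24 h with a 12 h tolerance, so at most 24 + 12 = 36 h. The one hemolysis marker specified, haptoglobin, is measured at arrival.
4. Delayed immunologic complications in Section 6.1: 4. Number that are named endpoints in Section 2.8: 0.

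**Routes of capture after 48 hours**

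| Route | What it catches | Delayed immunologic reactions, by arm? |
|---|---|---|
| Section 2.8 secondary outcomes | Organ failure, ARDS, pneumonia and blood stream infection, mortality, acute hemolytic reactions | No; they do not identify these reactions or assess relatedness |
| Section 2.9 and Appendix 8, Table 4 | Hemolytic transfusion reactions, with neither the acute qualifier nor a time limit | Delayed hemolysis could be entered, but this conflicts with the acute-only definition in Section 2.8 and sets out no way of finding cases |
| Discharge summary (Section 6.4.5) | Common major complications | Recorded but not handled as adverse events, so no relatedness review |
| Section 6.4.2 and the Section 6.4.6 table | Reporting deadlines, with no stated time window | They govern events already found and create no surveillance |
| Transfusion-reaction procedure (Section 6.4.6) | Mainly reactions noticed during transfusion | Results go to the medical record and blood bank; no route to a comparison by arm |
| Donor look back (Section 6.4.6, Appendix 6) | Infection later found in a donor | Does not address immunologic reactions; no route to the trial data or DSMB is named |

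No route collects all four listed reactions by arm after 48 hours. Only delayed hemolysis has a possible entry point, and that depends on which of two definitions is applied.

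**How much could be at stake**

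The documents give neither onset times nor rates. As an assumption, let *p* be the true chance that a patient in one arm has such a reaction after 48 hours. With 56 patients per arm (Section 2.9) and independent patients, the chance of at least one is 1 − (1 − *p*)^56:

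- *p* = 0.1%: 5.4%
- *p* = 1%: 43.0%
- *p* = 5%: 94.3%

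The range is too wide to serve as an estimate. Even with complete capture, zero events among 56 would exclude, at the upper limit of a two-sided 95% interval, only rates above 1 − 0.025^(1/56) = 6.4%. Better collection would make a zero interpretable, but it would not make the pilot informative about rare events. No sample-size or power figure changes.

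**The case against.** The strongest reply is that adverse-event monitoring is only one part of the safety plan. The primary safety outcome is mortality. Sections 2.8 and 2.9 take it at 28 days, while the data analysis plan in Section 6.4.2 and Appendix 8, Table 2 take it in hospital; neither definition stops at 48 hours. Organ failure, ARDS and infection are compared to 28 days or discharge, and the DSMB sees those comparisons too. Serious unexpected related events are reportable with no stated time limit, and donor infections have their own tracing process. All of this stands.

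A reader might therefore go too far in three ways:

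- **That harms of the study product in general are missed by design, or that the trial's safety conclusion rests on 48 hours.** The documents do not support this, for the reasons just given and because acute reactions fall well inside the window.
- **That transmitted infection belongs in the same gap.** Section 6.1 lists it separately, without the delayed label, and look back covers it.
- **That only the whole-blood arm is exposed.** Section 6.1 presents the list as applying to any transfusion. Controls may receive red cells before arrival, with uncrossmatched units available in the emergency department (Section 2.5), and Appendix 1 allows base units of either Rh type.

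It is also fair to say that passive collection to 28 days would be incomplete. No late sample or antibody screen is planned, and the 28-day check may be chart review, patient contact or a death index. That limits what the remedy can deliver. It does not justify a collection rule that leaves out listed harms altogether.

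**Conclusion.** The point holds in a narrow form. The four delayed immunologic reactions in Section 6.1 have no prospective collection by arm, and no relatedness review, after 48 hours. A null comparison of adverse-event rates gives no information on those that appear later. The primary safety conclusion and the comparisons of organ failure, ARDS, nosocomial infection and death are unaffected.

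The 7.1% figure describes the calendar only; it is not the share of events captured. That some reactions fall after 48 hours is inferred from the protocol's own word for them, since no onset times are given. The number missed cannot be sized from the documents and, with 56 patients per arm, may be zero. The change is worth making because safety is a stated objective and the cost is low.

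**What to change.** 1. Keep general adverse-event monitoring at 48 hours.
2. In both arms, collect transfusion-related adverse events and serious adverse events to 28 days or discharge: the four listed delayed reactions, including red-cell antibodies found in routine testing, and any look-back notification. Use chart review and blood-bank reports.
3. Apply the same relatedness review as in the first 48 hours, and show these events by arm to the DSMB.
4. State that ascertainment after 48 hours is passive, so that a zero is not read as the result of active screening. Hemolytic disease in a future pregnancy remains outside any of these windows.
5. Reconcile the acute-only hemolysis endpoint in Section 2.8 with the unqualified hemolytic reactions in Section 2.9 and Appendix 8, Table 4, and give the outcome one definition and one time window.

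The cost is protocol wording, a few CRF fields and some added chart-review work. No new visits or samples are needed, and treatment, sample size and power do not change.
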